9.4.4. Immunogenicity Assessments

Samples for immunogenicity testing will be collected at time points indicated in the Schedule of Activities (Section 2). Venous blood samples will be collected into tubes and used to determine antibody production against ixekizumab. The actual date of each sampling will be recorded on the laboratory requisition.

Immunogenicity will be assessed by a validated assay designed to detect ADAs in the presence of ixekizumab. Antibodies may be further characterized and/or evaluated for their ability to neutralize the activity of ixekizumab. Treatment-emergent immunogenicity is defined as any occurrence of a 4-fold or 2 dilution increase in titer over the pretreatment baseline titer. In the case of a negative result at baseline, treatment-emergent immunogenicity is defined as an increase in titer to $\geq 1:10$. Immunogenicity samples will also be analyzed for ixekizumab serum concentration to facilitate the interpretation of the immunogenicity data at Week 12 (Visit 6), Week 20 (Visit 10) and ETV.

In the event of serious drug hypersensitivity reactions (such as generalized urticaria and/or anaphylaxis), additional samples will be collected as close to the onset of the event as possible and approximately 30 days following the event to evaluate antidrug antibodies (ADA), LY2439821 serum concentration, and additional exploratory biomarkers of hypersensitivity which could include tryptase, complement levels and cytokine measurements.

Samples will be retained for a maximum of 15 years after the last patient visit, or for a shorter period if local regulations and ERBs allow, at a facility selected by the sponsor. The duration allows the sponsor to respond to future regulatory requests related to ixekizumab. Any samples remaining after 15 years will be destroyed.

9.4.5. Other Safety Measures

9.4.5.1. Physical Exam

One complete physical examination (excluding pelvic, rectal, and breast examinations) will be performed at screening. This examination will determine whether the patient meets the criteria required to participate in the study and will also serve as a monitor for pre-existing conditions and as a baseline for treatment-emergent adverse event (TEAE) assessment. All physical examinations throughout the study should include a symptom-directed physical evaluation, as well as an examination of the heart, lungs, abdomen, and a visual examination of the skin.

9.4.5.2. Chest X-Ray and Tuberculosis Testing

A posterior-anterior view chest X-ray will be obtained, unless the X-ray or results from a chest X-ray obtained within 6 months prior to the study are available. The chest X-ray will be obtained locally. The chest X-ray or results will be reviewed by the investigator or designee to exclude patients with active TB infection. In the opinion of the investigator, if evaluating chest X-ray is medically necessary, the investigator may do so any time during the study.

In addition, patients will be locally tested at screening and at visits, as indicated on the Schedule of Activities (Section 2) for evidence of active or latent TB indicated by a positive purified protein derivative (PPD) skin-test response (≥ 5 mm induration, between approximately 48 and

72 hours after test application, regardless of BCG vaccination history). If, in the judgment of the investigator, an interferon gamma release assay (QuantiFERON-TB Gold test) is preferred as an alternative to the PPD skin test for the evaluation of TB infection, it may be used instead of the PPD test (positive tests excluded) and would be read locally. If an interferon gamma release assay (QuantiFERON-TB Gold test) is indeterminate, 1 retest is allowed. The same method should be used at the retest. If the retest is indeterminate, then the patient is excluded from the study.

Patients with documentation of a negative test result within 3 months prior to baseline (Week 0; Visit 2) do not need a TB screen at Visit 1. Documentation of this test result must include a record of the size of the induration response. A PPD test recorded as negative without documenting the size of induration will result in a retest.

However, patients with a PPD skin test ≥ 5 mm induration or a positive QuantiFERON-TB Gold test at screening, but no other evidence of active TB, may be rescreened 1 time and may be enrolled without repeating the PPD or QuantiFERON-TB GOLD test if the following conditions are met:

- after receiving at least 4 weeks of appropriate latent TB infection (LTBI) therapy,
- having no evidence of hepatotoxicity (ALT/AST must remain ≤ 2 times ULN) upon retesting of serum ALT/AST prior to administration of investigational product. Such patients must complete appropriate LTBI therapy during the course of the study in order to remain eligible, and
- meeting all other Inclusion/Exclusion criteria for participation.

Patients who have a documented history of completing an appropriate TB treatment regimen with no history of re-exposure to TB since their treatment was completed and no evidence of active TB are eligible to participate in the study. These patients should not undergo TB testing at screening or at later scheduled visits in the study, as per the Schedule of Activities (Section 2).

Patients who have had household contact with a person with active TB are excluded, unless appropriate and documented prophylaxis for TB was given.

9.4.5.3. Columbia-Suicide Severity Rating Scale

The C-SSRS is a scale that captures the occurrence, severity, and frequency of suicidal ideation and/or behavior during the assessment period. The scale includes suggested questions to solicit the type of information needed to determine if suicidal ideation and/or behavior occurred. The C-SSRS is administered by an appropriately trained healthcare professional with at least 1 year of patient care/clinical experience. The tool was developed by the National Institute of Mental Health trial group (TASA) for the purpose of being a counterpart to the Columbia Classification Algorithm of Suicide Assessment categorization of suicidal events. Patients will be assessed according to the Schedule of Activities (Section 2). The Self-Harm Supplement Form is a 1-question form that asks for the number of suicidal or nonsuicidal self-injurious behaviors the patient has experienced since the last assessment. For each unique event identified, a questionnaire (Self-Harm Follow-Up Form) which collects supplemental information on the self-

injurious behavior is to be completed. The Self-Harm Supplement Form will be completed according to the Schedule of Activities (Section 2).

The non-leading AE collection should occur prior to the collection of the C-SSRS. If a suicide-related event is discovered during the C-SSRS, but was not captured during the non-leading AE collection, sites should not change the AE form. If an event is serious or leads to discontinuation, this is an exception where the SAE and/or AE leading to discontinuation should be included on the AE form and the process for reporting SAEs should be followed.

9.4.5.4. Hepatitis B Screening

Patients who test HBsAg, HBcAb+ in conjunction with positive confirmatory HBV DNA test, or have positive HBV DNA test, regardless of HBsAb status, at screening will be excluded.

If an enrolled patient is positive for HBsAb and/or HBcAb, and negative for HBV DNA, the HBV DNA needs to be checked at least once every month in Periods 2 and 3 (See Section 2).

In addition to the above, any enrolled patient who is HBcAb+ and/or HBsAb+ and who experiences an elevated ALT or AST level >3x ULN must undergo HBV DNA testing. If the HBV DNA test is negative, the investigator should consult with the Lilly-designated medical monitor regarding further management of the patient.

If the result of the HBV DNA testing is positive, the patient must be discontinued from the study and should receive appropriate follow-up medical care, including consideration for antiviral therapy. A specialist physician in the care of patients with hepatitis (for example, infectious disease or hepatologist subspecialists) should be consulted and potentially start antiviral therapy prior to discontinuation of any immunosuppressant therapy (including study drug). Timing of discontinuation from the study and of any immunosuppressant therapy (including study drug) needs to be based on the recommendations of the consulting specialist physician in conjunction with the investigator and medical guidelines/standard of care.

9.4.5.5. Hepatitis C Screening

Patients who test positive for HCV antibody and have a positive confirmatory HCV RNA test at screening will be excluded.

Patients with a previous diagnosis of hepatitis C who have been treated with antiviral therapy and achieved a sustained virologic response may be eligible for inclusion in the study, provided they have no detectable RNA on the screening HCV RNA test for this protocol. A sustained virologic response is defined as an undetectable HCV RNA level, 12 weeks after completion of a full, documented course of an approved antiviral therapy for HCV.

Patients who have spontaneously cleared HCV infection, defined as (i) a positive HCV antibody test and (ii) a negative HCV RNA test, with no history of anti-HCV treatment, may be eligible for inclusion in the study, provided they have no detectable HCV RNA on screening for this study, *and* no detectable HCV RNA on the screening HCV RNA test for this protocol.

Any patient with a history of HCV infection who develops elevated ALT >3x ULN will be tested for HCV RNA.

Any patient diagnosed with hepatitis C during the study will be discontinued from the study and should receive appropriate follow-up medical care.

9.4.6. Safety Monitoring

Lilly will periodically review evolving aggregate safety data within the study by appropriate methods.

9.4.6.1. Neutropenia

patient with neutrophil (segmented) counts <1500 cells/ μL should be managed for neutropenia as follows:

- <500 cells/ μL , see Discontinuation Criteria (Section 8.1)
- ≥ 500 cells/ μL and <1000 cells/ μL , see Discontinuation Criteria (Section 8.1)
- ≥ 1000 cells/ μL and <1500 cells/ μL , and the patient has a concurrent infection that requires systemic anti-infective therapy (for example, antibiotic, antifungal agent, antiviral agent):
 - The dose of investigational product should be withheld, the patient should receive appropriate medical care, and a repeat test for neutrophil count should be performed within 4 weeks from knowledge of the initial report. If the repeat neutrophil count has returned to ≥ 1500 cells/ μL , and the infection has resolved or is resolving, the patient may resume dosing of investigational product and evaluation at scheduled visits. If the neutrophil count remains ≥ 1000 cells/ μL and <1500 cells/ μL , investigational product should continue to be withheld and a repeat neutrophil count should again be performed within another 4 weeks. If, after 2 repeat tests, the neutrophil count still remains ≥ 1000 cells/ μL and <1500 cells/ μL , and:
 - a. the infection has not fully resolved, the patient will be discontinued from the study.
 - b. the infection has resolved, the patient may resume dosing and evaluation at scheduled visits. However, if resumption of dosing is not deemed appropriate by the investigator, the patient will be discontinued from the study. Patients who discontinue the study continue to the ETV.
- ≥ 1000 cells/ μL and <1500 cells/ μL , and the patient has no concurrent infection that requires systemic anti-infective therapy (for example, antibiotic, antifungal agent, antiviral agent):
 - Dosing may continue, and a repeat neutrophil count should be performed 4 to 8 weeks from knowledge of the initial report. Testing may be at a regularly scheduled visit or at an unscheduled visit, as necessary.

Repeat testing should be performed at 4- to 8-week intervals until the neutrophil count has returned to ≥ 1500 cells/ μL . If the patient has 3 or more post-baseline neutrophil counts of ≥ 1000 cells/ μL and <1500 cells/ μL , no value of <1000 cells/ μL , and no post-baseline infection requiring systemic anti-infective therapy, the patient may continue or resume further evaluation at scheduled visits, as deemed appropriate by the investigator.

If a patient without initial concurrent infection develops an infection that requires systemic anti-infective therapy, then the patient should be managed as indicated above for patients with concurrent infection.

9.4.6.2. Hepatic Safety Monitoring

If a study patient experiences elevated ALT $\geq 3X$ ULN, ALP $\geq 2X$ ULN, or elevated TBL $\geq 2X$ ULN, liver testing ([Appendix 4](#)) should be repeated within 3 to 5 days including ALT, AST, ALP, TBL, direct bilirubin, gamma-glutamyl transferase, and creatine kinase to confirm the abnormality and to determine if it is increasing or decreasing. If the abnormality persists or worsens, clinical and laboratory monitoring should be initiated by the investigator and in consultation with the study medical monitor. Monitoring of ALT, AST, TBL, and ALP should continue until levels normalize or return to approximate baseline levels.

Hepatic Safety Data Collection

Additional safety data should be collected via the electronic case report form (CRF) if 1 or more of the following conditions occur:

- elevation of serum ALT to $\geq 5X$ ULN on 2 or more consecutive blood tests
- elevated serum TBL to $\geq 2X$ ULN (except for cases of known Gilbert's syndrome)
- elevation of serum ALP to $\geq 2X$ ULN on 2 or more consecutive blood tests
- patient discontinued from treatment due to a hepatic event or abnormality of liver tests
- hepatic event considered to be a SAE

See Section [9.4.5.4](#) with regards to hepatitis B monitoring.

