| 12-lead ECG ⁿ | X | | | | | | | | | | |
| FSH ^o | X | | | | | | | | | | |
| HIV/HBV/HCV ^p | X | | | | | | | | | | |
| HBV DNA ^q | X | | | X | X | X | | X | | X | X |
| Serum pregnancy test (Women of childbearing potential [WCBP] only) ^r | X | | | | | | | | | | |

| Procedure | Screening Period (Period 1) | Treatment Period - Induction (Period 2) | | | | | Treatment Period - Maintenance (Period 3) | | | | ETV |
|---|-----------------------------|---|---------|---------|---------|---------|---|----------|----------|----------|-----|
| | | V1 | V2 | V3 | V4 | V5 | V6 | V7 | V8 | V9 | |
| Visit Number | V1 | V2 | V3 | V4 | V5 | V6 | V7 | V8 | V9 | V10 | ETV |
| Study Week | - | 0 | 2 | 4 | 8 | 12 | 14 | 16 | 18 | 20 | |
| Visit Intervals | -30d to -7d | 0 | 14 ± 2d | 28 ± 4d | 56 ± 4d | 84 ± 2d | 98 ± 2d | 112 ± 2d | 126 ± 2d | 140 ± 2d | NA |
| Urine pregnancy test (WCBP only) ^r | | | | | | X | | | | X | X |
| Clinical chemistry | X | X | | | | X | | | | X | X |
| Hematology | X | X | | | | X | | | | X | X |
| Urinalysis | X | | | | | X | | | | X | X |
| hsCRP | | X | | | | X | | | | X | X |
| Beta-D-glucan ^s | X | | | | | | | | | | |
| KL-6 ^t | X | | | | | | | | | | |
| Immunogenicity testing ^u | | X | | | | X | | | | X | X |
| LY2439821 serum concentration ^{uv} | | | | | | X | | | | X | X |
| Pharmacogenetic sample (genetic sample/DNA) | X | | | | | | | | | | |

Abbreviations: AE = adverse event; AESI = adverse event of special interest; BP = blood pressure; BSA = body surface area; C-SSRS = Columbia- Suicide Severity Rating Scale; d = days; DLQI = Dermatology Life Quality Index; DNA = deoxyribonucleic acid; ECG = electrocardiogram; ETV = early termination visit; FSH = follicular stimulating hormone; GPP = generalized pustular psoriasis; HBcAb = hepatitis B core antibody; HBsAb = hepatitis B surface antibody; HBV = hepatitis B virus; HCV = hepatitis C virus; HIV = human immunodeficiency virus; hsCRP = high sensitivity C-reactive protein; IL-36 RN = interleukin 36 receptor antagonist; IP = investigational product; KL-6 = Kerbs von Lungren 6 antigen; NA = not applicable; NRS = numeric rating scale; PASI = Psoriasis Area and Severity Index; PCP = pneumocystis pneumonia; PPD = purified protein derivative; Ps = psoriasis; PSSI = Psoriasis Scalp Severity Index; SAE = serious adverse event; SC = subcutaneous; sPGA = static Physician's Global Assessment; TB = tuberculosis; V = study visit.

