8.1. Discontinuation from Study Treatment

8.1.1. *Permanent Discontinuation from Study Treatment*

Possible reasons leading to permanent discontinuation of investigational product:

- **Patient Decision**
 - the patient requests to discontinue investigational product.
- **Discontinuation due to a hepatic event or liver test abnormality.** A patient who is discontinued from investigational product due to a hepatic event or liver test abnormality should have additional hepatic safety data collected via CRF.

Discontinuation of the investigational product for abnormal liver tests **should be** considered by the investigator when a patient meets one of the following conditions after consultation with the Lilly designated medical monitor:

- ALT or AST >8X ULN
- ALT or AST >5X ULN for more than 2 weeks
- ALT or AST >3X ULN and total bilirubin level (TBL) >2X ULN or international normalized ratio (INR) >1.5
- ALT or AST >3X ULN with the appearance of fatigue, nausea, vomiting, right upper-quadrant pain or tenderness, fever, rash, and/or eosinophilia (>5%)
- alkaline phosphatase (ALP) >3X ULN
- ALP >2.5X ULN and TBL >2X ULN
- ALP >2.5X ULN with the appearance of fatigue, nausea, vomiting, right quadrant pain or tenderness, fever, rash, and/or eosinophilia (>5%)
- In addition, a patient who meets any one of the following criteria should be discontinued from the investigational product and conduct ETV, and discontinue from the study:
 - Absolute neutrophil (segmented) counts (see safety monitoring for neutropenia; Section 9.4.6.1):
 - <500 cells/ μ L
 - \geq 500 and <1000 cells/ μ L (based on 2 test results; the second test performed within 1 week from knowledge of the initial result).
 - \geq 1000 and <1500 cells/ μ L (based on 3 test results as specified in Section 9.4.6.1) - AND - an infection that is not fully resolved.
 - Total WBC count <2000 cells/ μ L (<2.00 x 10³/ μ L).
 - Lymphocyte count <500 cells/ μ L (<0.50 x 10³/ μ L).
 - Platelet count <50,000 cells/ μ L (<50 x 10³/ μ L).

- The patient experiences a severe AE, an SAE, or a clinically significant change in a laboratory value occurs that, in the opinion of the investigator, merits the discontinuation of the investigational product.
- Clinically significant systemic hypersensitivity event following administration of investigational product that does not respond to symptomatic medication or results in clinical sequelae.
- The patient becomes pregnant.

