9.2.2. Adverse Events of Special Interest

The following AEs of special interest (AESIs) will be used to determine the safety and tolerability of ixekizumab over the range of doses selected for this clinical study.

Adverse events of special interest for ixekizumab are:

- cytopenias (leukopenia, neutropenia, and thrombocytopenia)
- liver function test changes/enzyme elevations (ALT, AST, bilirubin, and alkaline phosphatase)
- infection
- injection-site reactions
- allergic reactions/hypersensitivities
- cerebrocardiovascular events
- malignancies
- inflammatory bowel disease
- depression
- interstitial lung disease (ILD).

If infections, injection-site reactions, or allergic/hypersensitivity reactions are reported, sites will provide details on these events as instructed on the CRF. Investigators will also educate patients and/or caregivers about the symptoms of allergic/hypersensitivity reactions and will provide instructions on dealing with these reactions. A blood sample will be collected when possible for any patient who experiences an AE of allergic/hypersensitivity reactions during the study.

Data on preferred terms associated with cerebrocardiovascular events (defined as death, cardiac ischemic events including MI and hospitalization for unstable angina, hospitalization for heart failure, serious arrhythmia, resuscitated sudden death, cardiogenic shock, coronary revascularization procedure, stroke/transient ischemic attack, peripheral revascularization procedure, and peripheral arterial event and hospitalization for hypertension) will be collected, and these events and any deaths will be adjudicated by an external Clinical Events Committee (CEC) made up of a chairman, 2 cardiologists, and a neurologist.

Data on suspected IBD, as identified by events possibly indicative of ulcerative colitis and Crohn's disease, will be collected and the events will be adjudicated by an external CEC with expertise in IBD.

The role of external CECs is to adjudicate defined clinical events in a blinded, consistent, and unbiased manner throughout the course of a study. The purpose of the CEC for adjudication of cerebrocardiovascular events and the CEC for adjudication of suspected IBD events is to ensure that all reported events are evaluated uniformly by a single group.

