##### 6.13.4.1. Hepatic Tests

Categories in abnormal hepatic laboratory test results (including scheduled visits, unscheduled visits, and repeat measurements) using Performing Lab Reference Ranges are defined as:

- Abnormal alanine aminotransferase (ALT) or aspartate aminotransferase (AST):  $>1 \times$  upper limit of normal (ULN) to  $<3 \times$  ULN,  $\geq 3 \times$  ULN to  $<5 \times$  ULN,  $\geq 5 \times$  ULN to  $<10 \times$  ULN,  $\geq 10 \times$  ULN to  $<20 \times$  ULN, and  $\geq 20 \times$  ULN
- Total bilirubin:  $>1 \times$  ULN to  $<1.5 \times$  ULN,  $\geq 1.5 \times$  ULN to  $<2 \times$  ULN, and  $\geq 2 \times$  ULN.
- Alkaline phosphatase (ALP):  $>1 \times$  ULN to  $<1.5 \times$  ULN, and  $\geq 1.5 \times$  ULN.

In addition, a by-patient listing of patients who meet any of the following criteria will be provided (Analysis population: FAS Population):

- Elevated hepatic criteria: defined as maximum ALT  $\geq 3 \times$  ULN and maximum total bilirubin  $\geq 2 \times$  ULN within the same study period
- An ALT or AST  $\geq 3 \times$  ULN
- A total bilirubin  $\geq 2 \times$  ULN
- An ALP  $\geq 1.5 \times$  ULN

The listing will include the following information: patient demographics, concomitant medications, ALT/AST/total bilirubin/ALP/ GGT by visit, treatment start and stop dates, and reason for treatment discontinuation.

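### The liver retest trigger in Protocol 9.4.6.2 leaves out AST, so one AST condition for considering a stop in 8.1.1 may have no second AST specifically called for until dosing is over

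*Protocol*

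**What the plan says.** **Retest rule.** Protocol 9.4.6.2 opens: "If a study patient experiences elevated ALT $\geq 3X$ ULN, ALP $\geq 2X$ ULN, or elevated TBL $\geq 2X$ ULN, liver testing" is to be repeated in 3 to 5 days. The repeat includes AST. If the abnormality persists or worsens, monitoring of ALT, AST, TBL and ALP continues until levels are normal or close to baseline.

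**Stopping conditions.** Protocol 8.1.1 lists seven liver conditions under which stopping should be "considered by the investigator when a patient meets one of the following conditions after consultation with the Lilly designated medical monitor". Four of the seven name ALT or AST. One of them is "ALT or AST >5X ULN for more than 2 weeks". Another is "ALT or AST >3X ULN and total bilirubin level (TBL) >2X ULN or international normalized ratio (INR) >1.5".

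**Schedule.** In the Schedule of Activities (Section 2) the chemistry row reads "Clinical chemistry | X | X | | | | X | | | | X | X". This places draws at screening, Week 0, Week 12, Week 20 and the ETV. Weeks 14, 16 and 18 have none.

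**AST elsewhere.** The list of adverse events of special interest (9.2.2) includes "liver function test changes/enzyme elevations (ALT, AST, bilirubin, and alkaline phosphatase"). For patients positive for hepatitis B core or surface antibody, 9.4.5.4 covers anyone "who experiences an elevated ALT or AST level >3x ULN must undergo HBV DNA testing". SAP 6.13.4.1 grades AST together with ALT and lists patients with either at 3X ULN or above.

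**The concern.** The sponsor has set AST thresholds for considering a stop, and one of them is defined by duration. The rule that would produce the second value does not respond to AST. A rise in ALT, ALP or TBL leads to a repeat within days and then to monitoring. A rise in AST alone leads, under 9.4.6.2, to nothing until the next scheduled draw.

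The protocol is more explicit for neutrophils. Where 8.1.1 depends on repeated counts, it or 9.4.6.1 says when the repeats are due. AST has no equivalent.

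At stake is a prompt to consider stopping while doses remain. By Week 20 a second AST could show that the two-week condition was met, but no dose would be left to withhold.

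**Working it through.** The plan states no figure on this point. The check sets the rules side by side and counts days.

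**1. Which AST conditions in 8.1.1 can be judged from the Week 12 visit?**

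| Condition naming AST | Data needed | Available at Week 12? |
|---|---|---|
| >8X ULN | one AST | yes |
| >5X ULN for more than 2 weeks | a further AST more than 14 days later | no |
| >3X ULN with TBL >2X ULN or INR >1.5 | AST, with TBL or INR | TBL yes, INR no |
| >3X ULN with symptoms or eosinophilia | AST, clinical review, hematology | yes |

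The second row is the gap that comes from leaving AST out of the trigger. The third row differs. TBL is on the Week 12 panel, and TBL at 2X ULN or above starts the retest itself. INR is not on the scheduled panel (Appendix 2), nor among the tests that 9.4.6.2 names for the repeat. It appears as a test only in Appendix 4. It is therefore not expressly required even when ALT is raised, and the AST omission is not the cause.

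**2. Time to the next scheduled AST, for a patient who stays to Week 20.** Week 12 is Day 84 ± 2 and Week 20 is Day 140 ± 2 (Section 2).

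- Nominal: 140 − 84 = 56 days
- Shortest: 138 − 86 = 52 days
- Longest: 142 − 82 = 60 days

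A patient who met the trigger would be repeated in 3 to 5 days.

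**3. Doses in that interval.** After the Week 12 visit, doses fall at Weeks 14, 16 and 18 (Days 98, 112 and 126): 3 × 80 mg = 240 mg. Counting from the Week 12 draw on nominal days:

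- Week 14: 98 − 84 = 14 days, not more than two weeks
- Week 16: 112 − 84 = 28 days
- Week 18: 126 − 84 = 42 days

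The earliest whole day on which the two-week condition could be met, counting from the Week 12 draw, is Day 84 + 15 = 99. A later draw could therefore still inform the Week 16 and Week 18 doses.

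**4. Patients who leave earlier.** A patient who reaches GIS = 1 in Period 3 has the ETV in place of the scheduled visit (5.1), and the ETV includes chemistry. If that happens at Week 14, 16 or 18, the nominal gap is 14, 28 or 42 days and dosing has ended. Patients who stop treatment early also go to the ETV. The 52 to 60 days and three doses apply only to those who stay to Week 20.

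**5. How many patients.** Each Period 3 entrant contributes one Week 12 draw. Section 10.1 assumes about 5 continuing patients at most, and its target is 5 + 5 = 10. All 12 planned patients is the upper figure for the planned enrollment. It is not a ceiling, because 10.1 allows the sample size to increase. The documents give no rate of AST-only elevation, so no probability can be stated.

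**The case against.** **Other routes to an earlier test exist.** Under 9.2 the investigator must document review of every laboratory safety report. He or she must also follow medically important or drug-related adverse events until they resolve, stabilize or are explained. A marked AST rise recorded as an adverse event could well qualify. Appendix 4 tests, INR included, are open for any treatment-emergent hepatic abnormality and may be required after consultation. Appendix 2 note b allows repeat chemistry at any time. Section 8.1.1 separately covers a clinically significant laboratory change that the investigator thinks merits stopping, and the two-week condition itself implies a second test. All of this stands, and it makes the gap small. But each route rests on judgement, and 9.2 leaves the frequency of follow-up to the investigator. None fixes a repeat AST.

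**The hepatitis B rule already reacts to AST.** It does, but only in antibody-positive patients. It requires HBV DNA and, if that is negative, a consultation with the medical monitor. It does not require a repeat AST.

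**An ALT-based trigger may be a deliberate choice.** This has some force. The hepatitis C rule (9.4.5.5), the hepatic data-collection list in 9.4.6.2 and the SAP's combined ALT and bilirubin criterion all omit AST, and some AST rises are not hepatic. The documents do not show that the omission was an error. Even so, 8.1.1 counts AST whatever its source, and the repeat panel already includes creatine kinase to help with interpretation.

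**The scenario is narrow.** It needs AST above 5X ULN while ALT is below 3X, ALP below 2X and TBL below 2X on the same draw. That is correct.

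**Conclusion.** The point holds as a minor safety gap. For an AST-only rise at Week 12, the plan does not specifically call for the second AST that one of its own consider-stopping conditions needs. For a patient who stays to Week 20 that value comes 52 to 60 days later, after three further doses. This assumes that sites follow the written rules and order nothing extra.

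A reader might infer more, and the documents do not support it:

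- **That a mandatory stop would be missed.** The liver conditions ask only that stopping be considered, after consulting the medical monitor.
- **That testing is barred.** It is permitted throughout. The plan simply does not call for it.
- **That leaving AST out of the trigger disables two stopping conditions.** It accounts for one. The missing INR is a separate matter that exists with ALT raised as well.
- **That results would be distorted.** No efficacy or safety summary is affected. At most, the by-visit hepatic listing would show no scheduled value between Week 12 and Week 20 or the ETV.

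The change is a cheap improvement.

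**What to change.** In Protocol 9.4.6.2, change the trigger to: *ALT or AST ≥3X ULN, ALP ≥2X ULN, or TBL ≥2X ULN*. An AST-only rise then leads to the 3- to 5-day repeat and, if it persists, to the monitoring already described there. The two-week condition could then be judged from about Day 99, before the Week 16 and Week 18 doses. The 8.1.1 thresholds and its consider-stopping action stay as they are. No change is proposed to the hepatitis C rule or the hepatic data-collection list.

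Separately and optionally, add prothrombin time/INR to the named repeat tests when ALT or AST is above 3X ULN. The INR limb of 8.1.1 would then have a required test behind it.

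**Cost.** A minor amendment supplied to each site's ethics board (Appendix 3.1.3), best bundled with another. An AST-only rise means one extra draw, plus follow-up draws if it persists, including for some rises that prove not to be hepatic. When ALT is raised, INR is one more test on a draw already called for. It is already listed in Appendix 4 and may be run at the sponsor-designated or a local laboratory.
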